Study design:	
This is a non-interventional, multicentre, cohort study, based on new data collection, which will include a representative sample of patients with advanced/metastatic NSCLC in Greece.
 
Patients will be treated according to the local prescribing information of the study medication (afatinib, GIOTRIF®) and routine medical practice in terms of visit frequency and types of assessments performed. Since this is purely non-interventional study, primary data obtained prospectively during the study visits through patients' interview and patient reported outcomes (PROs) or as performed per standard clinical practice will mainly be employed.
 
The overall study duration period is expected to be 60 months, including a 48-month enrollment period and a minimum 12-month follow-up period. During the observation period, data will be collected at routine clinical visits at 2-month intervals for the first 12 months and at 6-month intervals thereafter until the end of study participation. The end of study participation is defined as a maximum of 48 months after afatinib treatment initiation or disease progression, death, withdrawal of consent, unacceptable toxicity, study completion or physician's decision whichever occurs earlier. The maximum 48-month length of participation in the study pertains to the patients enrolled during the first 12 months of recruitment, while the maximum observation period for the last patient enrolled is 12 months.

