	
The McNemar's test will be used in order to evaluate the change in the levels ('with problems'/'no problems') of each dimension between enrolment and the post-baseline visits.
 
The distribution of patients in the different ECOG performance status levels at every study time-point will be presented in frequency tables (N, %). Additionally, changes in the status of patients from baseline to post-baseline evaluations will be depicted in shift tables.
 
Adherence to study treatment along with proportion of patients who discontinued permanently or temporarily treatment, dose modifications and reasons for treatment discontinuations will be analysed in descriptive manner.
 
In order to examine the impact of baseline and other characteristics including among others, gender, age, BMI, educational/marital/employment status, disease stage, histological subtype, sites of metastases, EGFR mutation subtype, smoking status, ECOG PS, type of concomitant medications and comorbidity count, as well as adherence to therapy at 6 months on the study primary endpoint, generalized linear models will be applied.
 
In addition, the number and proportion of patients experiencing any serious AE (SAE) and the number and proportion of patients experiencing any non-serious AE (NSAE) will be calculated and presented in frequency tables by MedDRA system organ class (SOC) and preferred (PT) while frequency tables will be presented pertaining to the National Cancer Institute (NCI) Common Toxicity Criteria for Adverse Events (CTCAE) toxicity grade classification of AEs.
 
All the aforementioned statistical tests will be two-sided and will be performed at a 0.05 significance level.
 
Statistical analysis will be conducted using a validated statistical software package (e.g., SAS).
 
Taking into consideration the long-term study duration as well as the current limited evidence on the real-world clinical outcomes of treatment with afatinib in patients with NSCLC, an interim analysis is planned to be performed after the first enrolled 40 patients have completed the 6-month study observation period.
 
The main purpose of the interim analysis is to gain preliminary information on the impact of afatinib in the study key outcome measures. No resultant decisions and actions will be taken in terms of the study progress as a consequence of the interim analysis. The interim analysis does not involve any stopping boundary for early stop due to efficacy or for sample size adjustment, thus no multiplicity adjustment will be performed.

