#### **11.1.3.2 Secondary endpoints/outcome measures**

[figure not shown]
- Change in the total LCSS score, ASBI score and individual domain scores from enrolment to each post-baseline predefined timepoints; in addition change throughout the study observation period will be examined using longitudinal analysis;
- Proportion of patients (n, %) with reported problems for each level for each dimension of EQ-5D and proportion of patients with 'no problems' (i.e., level 1) and 'with

[figure not shown]
*problems'* (i.e., level 2 & 3) at enrolment and at the post-baseline predefined timepoints;

- EQ-visual analogue scale (VAS) score (mean  $\pm$  SD) at enrolment and at the post-baseline predefined timepoints;
- Change in the proportion of patients in each of the EQ-5D dimension levels (no problems, with problems) and change in the EQ-VAS score between enrolment and post-baseline predefined timepoints;
- Change in ECOG PS scores from baseline to post-baseline predefined timepoints;
- Ratio of doses actually taken to doses prescribed over the study participation period and reasons for discrepancies;
- Proportions of patients with treatment discontinuations, temporary interruptions, or dose change(s) and reasons for treatment modifications.

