#### **11.4.3 Other variables**

➤ ***Sociodemographic and anthropometric patient characteristics:***

- Age (years)
- Gender: *males, females (n, %); male-to-female ratio*
- Race: *Caucasian, Asian, African, other;*
- Place of residence: *urban areas, semi-urban areas, rural areas;*
- Educational level: *no education, primary education, secondary education, tertiary education;*
- Marital status: *single, married, divorced, widowed;*
- Employment status: *unemployed, employed, retired, household duties, other;*
- Smoking status: *never smoker, former smoker, occasional smoker, current smoker; if former or current smoker: smoking pack-years, and if former smoker: years since quitting smoking;*
- Weight (kg);
- Height (cm);
- Body mass index (BMI in kg/m^2);
- Systolic and diastolic arterial pressure (mmHg);
- Respiratory rate (bpm [breaths/minute]).

➤ ***Disease & clinical characteristics***

- Age at disease diagnosis;
- Disease stage (IIIB, IV) at baseline;
- Histologic classification (*adenocarcinoma squamous-cell-carcinoma, other*);
- EGFR mutation subtype (*exon 19 deletions, Leu858Arg, other*);
- Sites of metastases at baseline;
- Previous disease-related treatment patterns;
- Baseline comorbid conditions;
- Change in disease status throughout the study period.

➤ ***Treatment characteristics***

- Time from diagnosis to afatinib treatment onset;
- Length of exposure to afatinib treatment throughout study duration;
- Starting dosage regimen;
- Type of dose modifications over the study observation period;
- Concomitant medications both at baseline and throughout the conduct of the study.

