### **11.8.3 Analysis for the secondary endpoints**

With regard to the secondary endpoints pertaining to the LCSS outcome measures, the mean change of the total LCSS, defined as the average value of all individual item scores, will be calculated from enrolment to all available subsequent study visits and will be examined for statistical significance with the use of the paired t-test or its non-parametric analogue. Similar analysis will be performed for the ASBI subscore and each individual domain of LCSS.

If applicable, pertaining to the change of the mean LCSS as well as the mean ASBI through the observation period, linear mixed models will be applied, in order to estimate the monthly predicted change in the aforementioned scores.

Additionally, the symptom improvement rate throughout the study observation period will also be calculated in patient-years.

The distribution of patients by level ('level 1: no problems', 'level 2: some problems' and 'level 3: extreme problems') for each dimension (mobility, self-care, usual activities, pain/discomfort, anxiety/ depression) as well as the distribution of patients in the dichotomized EQ-5D levels ['no problems' (level 1) and 'problems' (levels 2 and 3)] will be presented in frequency tables (N, %) for all patients with available data. Descriptive statistical measures will be calculated for the EQ-VAS score at each predefined study time-point.

The McNemar's test will be used in order to evaluate the change in the levels ('with problems'/ 'no problems') of each dimension between enrolment and the post-baseline visits.

Descriptive statistics of the EQ-VAS will be presented for each study visit as well as for the observed changes in the EQ-VAS from the enrolment visit to each post-baseline study time-point; while the paired t-test or the Wilcoxon signed rank test will be used to assess the statistical significance of the change.

The distribution of patients in the different ECOG performance status levels at every study time-point will be presented in frequency tables (N, %). Additionally, changes in the status of patients from baseline to post-baseline evaluations will be depicted in shift tables.

Adherence to treatment with afatinib as well as the proportions of patients who discontinued or interrupted treatment, and those who underwent any dose modifications along with the type of dosage modifications and reasons for these, will be analysed in a descriptive manner.

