### **9.2 Adverse events**

The following adverse events are collected from the time the patient has signed the informed consent until the completion of his/her participation in the study: all serious and non-serious adverse drug reactions (ADRs) related to GIOTRIF; all AEs with fatal outcome (regardless of causal relationship with GIOTRIF); and all AEs (serious and non-serious) which are relevant to a serious ADR or to an AE with fatal outcome. An ADR is defined as a response to a medicinal product which is noxious and unintended. Response in this context means that a causal relationship between a medicinal product and an adverse event is at least a reasonable possibility.

All recorded adverse events will be mapped by LLT, PT and SOC according to MedDRA (the most updated version available at the time of coding onset). If two or more AEs (PTs) are reported as a unit, the individual terms will be reported as separate events.

A descriptive summary table will be created with the number and proportion of patients experiencing at least one adverse drug reaction regardless of seriousness (N)SADR, serious adverse drug reaction (SADR), non-serious adverse drug reaction (NSADR) and SAE. The percentage of patients who discontinued their treatment with afatinib due to AEs will also be tabulated.

Additionally, the following data will be provided in frequency tables:

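### In the public text, the proportions who discontinue, interrupt or change the dose of afatinib have no stated time point, although planned maximum observation runs from 12 to 48 months by enrolment date

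*Protocol*

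**What the plan says.** Patterns of afatinib use are a named secondary objective (Protocol 10.2, SAP 2.1.2). The matching endpoint in Protocol 11.1.3.2 reads "Proportions of patients with treatment discontinuations, temporary interruptions, or dose change(s) and reasons for treatment modifications", and the SAP lists it without a time point as well (2.1.2 and 2.2.1.2). Protocol 11.8.3 covers "the proportions of patients who discontinued or interrupted treatment, and those who underwent any dose modifications" and asks only for a descriptive analysis. The abstract does the same for the "proportion of patients who discontinued permanently or temporarily treatment, dose modifications and reasons for treatment discontinuations will be analysed in descriptive manner". SAP 9.2 adds, for safety: "The percentage of patients who discontinued their treatment with afatinib due to AEs will also be tabulated".

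The nearest wording that implies a period is next to this endpoint, not in it. The adherence endpoint is the "Ratio of doses actually taken to doses prescribed over the study participation period and reasons for discrepancies", and Protocol 11.4.3 lists "Type of dose modifications over the study observation period". Both point to each patient's own time in the study.

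That time is unequal by design. Enrolment lasts 48 months of a 60-month study. "The maximum 48-month length of participation in the study pertains to the patients enrolled during the first 12 months of recruitment", and the last patient enrolled has at most 12 months (Protocol abstract, study design; SAP 2.3). Participation can also end earlier, for example through progression, death or toxicity.

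SAP Section 8, which should hold the secondary-endpoint analyses, is not in the public copy. The text goes from Section 7 to Section 9, and Section 7 refers the adherence analysis to Section 8.2.

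**The concern.** A patient still on afatinib when observation ends administratively counts as not discontinued, whether that happens at month 12 or month 48. With no horizon, the percentage mixes drug and disease behaviour with the enrolment curve. Two studies with identical discontinuation risk but different accrual would report different figures.

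Protocol 9.3 wants the study to complement trial evidence and help clinicians decide. A discontinuation percentage drawn from 12 to 48 months of potential observation is hard to set beside another cohort's figure unless the period is known.

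The plan deals with unequal follow-up elsewhere. Symptom improvement gets a patient-years rate (Protocol 11.8.3), adverse drug reactions get exposure-adjusted rates with censoring (SAP 9.2), and imaging progression gets horizons from 6 to 48 months (SAP 6.2). The visible text gives treatment modification none of these.

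**Working it through.** The plan gives no figure for this endpoint, so there is none to reproduce. The check asks how far a crude proportion would sit from a fixed-time risk under the planned follow-up.

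**Inputs from the documents**
- Enrolment 48 months, study 60 months, maximum participation 48 months. For entry month e, planned maximum follow-up is C = min(48, 60 − e).
- Progression-free survival on afatinib (Protocol 9.2.1): a median of 13.6 months in one pivotal trial and 11.0 months in the other. The protocol calls the second figure a mean.

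**Assumptions**
- Entry is uniform over months 0 to 48.
- Time to permanent discontinuation is exponential with median m, so λ = ln 2 / m. Progression-free survival stands in for time on treatment.
- m = 11.0 and 13.6, the first being the stated mean treated as a median.

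**Follow-up.** Mean C = (12 × 48 + 36 × 30) / 48 = 34.5 months. One quarter of patients have the full 48 months.

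**Permanent discontinuation**
- Crude = [12(1 − e^(−48λ)) + 36 − (e^(−12λ) − e^(−48λ))/λ] / 48
- m = 11.0 (λ = 0.06301): (11.417 + 36 − 6.679) / 48 = 0.849
- m = 13.6 (λ = 0.05097): (10.961 + 36 − 8.945) / 48 = 0.792
- First-year enrolees: 1 − e^(−48λ)
- Last-year enrolees: 1 − (e^(−12λ) − e^(−24λ)) / (12λ)
- 12-month risk: 1 − e^(−12λ)

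| | m = 11.0 | m = 13.6 |
|---|---|---|
| Crude, all patients | 85% | 79% |
| First-year enrolees | 95% | 91% |
| Last-year enrolees | 67% | 59% |
| Risk at 12 months | 53% | 46% |
| Crude, front-loaded (triangular) entry | 91% | 86% |
| Crude, back-loaded (triangular) entry | 79% | 72% |

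Entry pattern alone moves the crude figure by 12 points (91.1 − 78.7) or 14 points (86.3 − 72.1). A milder front-loaded shape gives 89% and 84%.

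**Sensitivity to the mean.** If 11.0 months is a true exponential mean, the median is 11.0 × ln 2 = 7.6 months. The crude proportion is then 92% and the 12-month risk 66%.

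**Dose changes and reason-specific stops.** Here the event has hazard h and participation ends at rate λ. At constant h, cumulative incidence at t is h/(h+λ) × (1 − e^(−(h+λ)t)). All rates are illustrative, and ranges cover the two medians.

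| Assumed event hazard | Crude | At 12 months |
|---|---|---|
| 1% per month, constant | 12-14% | 8.0-8.5% |
| Constant, 20% by 12 months without other exits | 21-23% | 14-15% |
| Constant, 40% by 12 months without other exits | 38-42% | 29-31% |
| 3% per month for 3 months, then 0.3% | 10.7-11.4% | 9.4-9.7% |
| 15% per month for 3 months, then 0.5% | 36.5-37.6% | 35.0-35.7% |

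The early-weighted rows are plausible. Protocol 11.3.3 places diarrhoea mostly in the first two weeks and grade 3 diarrhoea mostly in the first six.

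**The case against.** Four arguments carry weight.

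- **The detail may be in text we cannot see.** Protocol 11.8 leaves the detailed methods to the SAP, and SAP Section 8 is withheld. The SAP sets 6- to 48-month horizons for imaging progression, so Section 8 may do so here. A reader might infer that the plan as a whole sets no horizon, but the public documents cannot show that. The gap is established for the protocol text, the SAP endpoint lists and SAP 9.2, which is visible.
- **The study is descriptive.** A reader might infer that the figure estimates nothing definable. That goes too far. A proportion over each patient's observation period is a legitimate count, and no test or comparison is attached to it. It is simply not a risk at a stated time.
- **Part of the remedy is already planned.** SAP 5.1 tabulates completion of each visit and withdrawals with reasons. SAP 3.7.1 and 9.1 summarise treatment duration and exposure net of interruptions. These help interpretation, but none gives a discontinuation or reason-specific proportion at a stated time.
- **Plain percentages are customary.** The abstract itself cites 5.9% of afatinib patients stopping for adverse events in a pivotal trial, without a horizon. That shows the convention and makes such comparisons likely. It does not remove the dependence on follow-up.

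It is also tempting to carry the size found for permanent discontinuation over to interruptions, dose changes and every reason for stopping. The last two rows of the second table show why that is unsafe.

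**Conclusion.** The point holds for the visible text. The modification proportions, and the percentage stopping for adverse events, are counts over planned maximum observation that ranges from 12 to 48 months, with no time point stated.

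For permanent discontinuation the consequence is material: the crude figure lies roughly 32-33 points above the 12-month risk, and last-year enrolees read 28-32 points below first-year enrolees with identical risk. These sizes rest on exponential times, uniform entry, and progression-free survival as a proxy that includes one mean used as a median. The direction does not depend on those choices. For events concentrated early the difference may be only 1-2 points. Nothing here affects the primary endpoint.

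**What to change.** - In Protocol 11.8.3, the abstract and SAP 9.2, report permanent discontinuation (overall and by main reason, including adverse events), first interruption and first dose change at 6 and 12 months from afatinib onset. The minimum 12-month follow-up gives every patient that potential observation by design. State how patients who leave observation before the horizon while still on treatment are counted.
- For permanent discontinuation beyond 12 months, use cumulative incidence censored at administrative end. Competing-risk curves for every event and reason are more than this descriptive endpoint needs.
- Keep the crude counts, shown beside observation time.
- Confirm that SAP Section 8.2 agrees, or align it.

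The cost is wording and a few more tables. Treatment modifications are already collected (Protocol 11.5), and onset and discontinuation dates already feed the duration variable in SAP 3.7.1. The headline percentages will be lower than the crude ones, and there will be more of them.

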## **7. AMENDMENTS AND UPDATES**

The main scope of Amendment #1 is: (a) to decrease the required sample size from 160 to 128; (b) to increase the length of the recruitment period by 12 months, i.e., from 36 to 48 months; (c) to increase the allowable time window of the study visits from  $\pm 1$  week for Visits 2-7, and  $\pm 2$  weeks for Visits 8-13 to  $\pm 3$  weeks for all; and (d) to include an interim analysis. The sections of the protocol that are affected, the description of the amendment and the reason for change are displayed in the following table, where deleted text is indicated by strikethrough and added text in bold characters:

Number	Date	Section of study protocol	Amendment or update	Reason
1	19 June 2018	Section 11.1 (Study Design), 4 th paragraph	
Text changed from:
 
“Follow-up visit frequency will be determined by the treating physician, however study-related data will be collected at 2-month (<math>\pm 1</math> week) intervals during the first 12 months of study participation and every 6 months (<math>\pm 2</math> weeks) thereafter until the end of the study observation period.”
 
to:
 
“Follow-up visit frequency will be determined by the treating physician, however study-related data will be collected at 2-month (<math>\pm 43</math> weeks) intervals during the first 12 months of study participation and every 6 months (<math>\pm 23</math> weeks) thereafter until the end of the study observation period.”
	To widen the time window for the scheduled study visits in order to allow for a data collection schedule that better mirrors the patterns of routine clinical care.
		Section 11.1.2 (Baseline and post-baseline timepoint definitions), 2 nd bullet	
Text changed from:
 
“Post-baseline predefined timepoints for study-specific assessments are defined as: every 2 months (<math>\pm 1</math> week) during the first 12 months of therapy and every 6 months (<math>\pm 2</math> weeks) thereafter until the end of patient’s participation in the study.”
 
to:
 
“Post-baseline predefined timepoints for study-specific assessments are defined as: every 2 months (<math>\pm 43</math> weeks) during the first 12 months of therapy and every 6 months (<math>\pm 23</math> weeks) thereafter until the end of
	To widen the time window for the scheduled study visits in order to allow for a data collection schedule that better mirrors the patterns of routine clinical care.

Number	Date	Section of study protocol	Amendment or update	Reason
			patient's participation in the study."	
		Section 11.2.1 (Site selection), 1 st paragraph	
Text changed from: “A total of 160 patients are planned to be enrolled by ten (10) Oncology and Pulmonology hospital centres/clinics in Greece specialized in lung cancer.”
 
to:
 
“A total of <del>160</del> 128 patients are planned to be enrolled by <del>ten (10)</del> seven (7) Oncology and Pulmonology hospital centres/clinics in Greece specialized in lung cancer.”
	To decrease the originally planned required sample size from 160 to 128 due to the lower than expected recruitment rate at the time of drafting this amendment, and the participation of fewer than projected study sites.
		Section 11.2.2 (Study time period), 1 st paragraph	
Text changed from: “The overall study duration period is expected to be 48 months, including a 36-month enrollment period and a minimum 12-month follow-up period.”
 
to:
 
“The overall study duration period is expected to be 48 60 months, including a 36 48-month enrollment period and a minimum 12-month follow-up period.”
	To extend the originally planned recruitment period by 12 months in order to facilitate the recruitment of the required sample size.
		Section 11.2.3 (Projected duration of patient participation in the study), 1 st paragraph	
Text changed from: “In the context of this study, each participant will be treated with afatinib until disease progression, death, withdrawal of consent, unacceptable toxicity, study completion or physician’s decision whichever occurs earlier. Thus the maximum
	To reflect the change in the overall study duration from 48 to 60 months due to the 12-month recruitment period

Number	Date	Section of study protocol	Amendment or update	Reason
			
length of participation in the study pertaining to the first enrolled patient is 48 months while the maximum observation period for the last patient enrolled is 12 months.”
 
to:
 
In the context of this study which is planned to have an overall duration of 60 months, each participant will be treated with afatinib and observed in the context of the study until the end of study participation defined as a maximum of 48 months after afatinib treatment initiation or until disease progression, death, withdrawal of consent, unacceptable toxicity, study completion or physician's decision whichever occurs earlier. Thus the The maximum 48-month length of participation in the study pertaining to pertains to the patients enrolled during the first enrolled patient is 48-12 months of recruitment, while the maximum observation period for the last patient enrolled is 12 months.”
	extension, and to clarify that the maximum observation period remains 48 months and has become applicable to patients enrolled over the first 12 months of recruitment.

Number	Date	Section of study protocol	Amendment or update	Reason
		Table 2 (Study Flow Chart and Assessments), “Visit Window” row	For Follow-up Visits V2 to V7, the visit window was changed from $\pm 1$ week to $\pm 3$ weeks; and for Follow-up Visits V8 to V13, the visit window was changed from $\pm 2$ weeks to $\pm 3$ weeks.	To widen the time window for the scheduled study visits in order to allow for a data collection schedule that better mirrors the patterns of routine clinical care.
		Section 11.6 (Study Size), 2 nd and 3 rd paragraphs	
Text changed from:
 
“...Consequently, the assessment of 120 patients is required to estimate the aforementioned proportion with accuracy (confidence interval) of <math>\pm 0.09</math> at the study population [95% CI: 0.41-0.59; <math>\alpha</math>: 0.05; Relative Standard Error (RSE): 9.1%].
 
In order to control for an estimated 25% drop out/non-evaluable rate, 160 patients are finally required in order to ensure the aforementioned sample size for the final statistical analysis.”
 
to:
 
“...Consequently, the assessment of <del>120</del> 96 patients is required to estimate the aforementioned proportion with accuracy (confidence interval) of <math>\pm 0.09</math> at the study population [95% CI: 0.41-0.59; <math>\alpha</math>: 0.05; Relative Standard Error (RSE): 9.1%]. with a margin of error not exceeding 0.10
	To reduce the originally planned evaluable study size from 120 to 96 patients which represents the minimum required size for estimating the primary outcome measure with the highest scientifically acceptable margin of error.

Number	Date	Section of study protocol	Amendment or update	Reason
			
which represents a scientifically acceptable level of precision of the estimate [95% CI: 0.40-0.60; <math>\alpha</math>: 0.05; Relative Standard Error (RSE): 10.21%]. This means that for any proportion between 0.05 and 0.95, the precision will range from 0.04 to 0.10 at a 95% confidence limit. The sample size determination has been performed using the statistical software package SAS v9.4 (SAS Institute, Cary, NC).
 
In order to control for an estimated 25% drop out/non-evaluable rate, 160 128 patients are finally required in order to ensure the aforementioned sample size for the final statistical analysis.”
	

Number	Date	Section of study protocol	Amendment or update	Reason
		Section 11.7 (Data Management), last paragraph	
Text changed from:
 
“Prior to the onset of data management activities, a detailed data management plan (DMP) will be issued describing the procedure to be followed for processing all collected study data in order to ensure they are valid, complete and accurate for statistical analysis. In addition, aiming at ensuring the expected quality of data, a thorough data cleaning session will be applied.”
 
to:
 
“Prior to the onset of data management activities, a detailed data management plan (DMP) will be issued describing the procedure to be followed for processing all collected study data in order to ensure they are valid, complete and accurate for the interim and final statistical analysis. In addition, aiming at ensuring the expected quality of data, a thorough data cleaning session will be applied twice during the conduct of the study for the purposes of the interim and final analysis, respectively.”
	To add text indicating that an interim analysis is planned to be conducted in the context of the study, and to update the relevant text pertaining to the data cleaning process to be applied.
		Section 11.8 (Data Analysis), 5 th paragraph	Text changed from :	To add a clarification that the SAP will also include details on the interim analysis to be carried out.

Number	Date	Section of study protocol	Amendment or update	Reason
			
lock.”
 
to:
 
“A SAP comprising a comprehensive and detailed description of the statistical methodology applied for the purposes of the <del>main analyses</del> interim and final analysis along with imputation methods for missing data will be prepared prior to database lock.”
	
		Section 11.8 (Data Analysis),	
Addition of new subsection #11.8.7 titled “Interim Analysis”
 
The text added under the new section follows:
 
“Taking into consideration the long-term study duration as well as the current limited evidence on the real-world clinical outcomes of treatment with afatinib in patients with NSCLC, an interim analysis is planned to be performed after the first enrolled 40 patients (i.e., around one-third of the overall sample size) have completed the 6-month study observation period (i.e., have attended the 6-month study visit [V4] or have discontinued study participation, whichever occurs first).
 
The main purpose of the interim analysis is to gain preliminary information on the impact of afatinib in the study key outcome measures. No resultant decisions and actions will be taken in terms of the
	To add a section indicating that an interim analysis is planned to be carried out in the context of this study, and to provide the rationale, the purpose and the process for handling the results of this analysis.

Number	Date	Section of study protocol	Amendment or update	Reason
			
study progress as a consequence of the interim analysis. The interim analysis does not involve any stopping boundary for early stop due to efficacy or for sample size adjustment, thus no multiplicity adjustment will be performed.
 
The confidentiality of the interim analysis data will be controlled by assignment of the analysis to a statistical group that is independent of the Sponsor and investigators, i.e. is not otherwise involved in the study design or conduct. After completion of the analysis the results will be summarized in a synoptic interim CSR and distributed to the study Sponsor. The detailed interim analysis results will not be disclosed to the participating investigators until the overall study completion in order to account for the avoidance of any bias that may result from the premature disclosure and subjective interpretation of the preliminary findings. However, the preliminary results may be announced in the form of an abstract or poster/presentation in a descriptive manner, as per the Sponsor's decision; in such case, the minimum required information will be disclosed aiming at safeguarding the scientific integrity of the final study
	

Number	Date	Section of study protocol	Amendment or update	Reason
			results.”	
		Section 8 (Milestones), Table 1	Update of the study milestones taking into consideration the actual date of first patient enrolled, the 12-month recruitment period extension and the incorporation of the interim analysis.	To update the study milestones in order to reflect the extension in the recruitment period, considering also the actual date of the first patient enrolled.
		Section 6 (Abstract)	Amendment of the relevant text that is affected by the aforementioned amendments in the main body of the protocol.	To harmonise the abstract section with all changes performed in the main body of the protocol as a result of this amendment.

